6.1 Research Question

The primary research question of this retrospective drug-utilisation study is to describe the pattern of use of lenalidomide in the clinical routine practice of MDS in countries of the EU in which

Revlimid (lenalidomide) is marketed for the treatment of patients with transfusion-dependent anaemia due to low- or intermediate-1-risk myelodysplastic syndromes associated with an isolated deletion 5q cytogenetic abnormality when other therapeutic options are insufficient or inadequate and where these patients have access to the drug post EU-approval for the MDS indication.

The study will also allow the collection of further information regarding the safety of lenalidomide within and outside of the EU approved indication (ie, in patients with any type of MDS other than transfusion-dependent IPSS low- or int-1-risk MDS with isolated del(5q)).

6.2 Research Objectives

6.2.1 *Primary Objective*

• To describe the pattern of use of lenalidomide in the clinical routine practice of MDS patients in the countries concerned

6.2.2 Secondary Objectives

- To further describe the safety of lenalidomide both within the EU approved indication [on-label cohort] and outside of the EU approved indication (ie, in patients with any type of MDS other than transfusion-dependent International Prognostic Scoring System [IPSS] low- or intermediate-1 [int-1]-risk MDS with isolated del(5q)) [off-label cohort], in terms of:
 - progression to AML
 - hematological and non-hematological adverse events, including infections, bleeding, thromboembolic events
 - major cardiac events and second primary malignancies (SPM) other than AML (which is considered as disease progression in patients with MDS)
 - evaluation of risk factors collected in the routine-care setting associated with progression to AML among MDS patients treated with lenalidomide within and outside of the EU approved indication, dependent on both sufficient patient numbers and availability of data within the selected data sources

7 RESEARCH METHODS

7.1 Study Design and Selection Criteria

7.1.1 Study Design

This is a post-authorisation, non-interventional, retrospective, drug-utilisation study. This study will be run in countries in the EU in which Revlimid (lenalidomide) will have been marketed in the new indication and where MDS patients will have access to the drug post EU-approval for the MDS indication. The only exception is that eligible patients from the company-sponsored Connect[®] Myeloid Disease Registry (US Cohort Registry) will be included regardless of start date of treatment to assess the secondary safety objectives (but not the primary drug-utilisation objective due to a different MDS indication approved in the US [see Section 7.4 for the US MDS approved indication]). Results from the selected data sources that represent at least 10 EU

countries, which have lenalidomide reimbursement, will be included. More EU countries will potentially be included, once they gain reimbursement.

This retrospective drug-utilisation study will include patients with MDS treated with lenalidomide, irrespective if within or outside the approved indication in the EU (eg, patients commencing lenalidomide treatment for transfusion-dependent IPSS low- or int-1-risk MDS with isolated del(5q) or with additional cytogenetic abnormalities, or IPSS risk categories int-2 or high, or patients with MDS without del(5q) will also be recorded). Both prevalent and incident MDS cases, defined as follows, are eligible for the inclusion into the retrospective drug-utilisation study:

Prevalent patients: patients whose initial MDS diagnosis is **prior** to the date of EU-approval for the MDS indication, but whose initiation of lenalidomide treatment occurs on or after the date of EU-approval for the MDS indication.

Incident patients: patients whose initial MDS diagnosis and initiation of treatment with lenalidomide is **after** the date of EU-approval for the MDS indication.

The sources of data for this study are described in Section 7.4.

The study is planned to collect retrospective data from subjects with MDS treated with lenalidomide according to the inclusion criteria, until at least 460 patients are included.

An interim descriptive report was prepared 1 year after study start. Within the interim descriptive report, available data on eligible patients regarding the pattern of use of lenalidomide within and outside the EU approved indication, namely the distribution of MDS patients according to predefined categories (eg, transfusion-dependent IPSS low- or int-1-risk MDS with isolated del(5q), or with additional cytogenetic abnormalities, or IPSS risk categories int-2 or high, or patients with MDS without del(5q)) was presented. On 29-Mar-2019, the first interim descriptive report was submitted to the Pharmacovigilance Risk Assessment Committee (PRAC) in order to discuss if the data collected on lenalidomide use, across different groups of MDS patients, are sufficient to allow successful completion of this study. The Assessment Report adopted by the CHMP on 27-Jun-2019 included a request to submit another interim descriptive report in Quarter (Q)1 2020. On 27-Mar-2020, the second interim descriptive report was submitted to PRAC (EMEA/H/C/000717/ANX/041.8). The final Assessment Report, adopted by the CHMP on 10-Dec-2020, concluded that the post-authorisation measure for the second interim report was fulfilled with no further action required.

The final data analysis will occur after at least 460 patients have been included and will be based on data from all eligible patients available at that time.

Data will be collected for both on- and off-label patients, to cover the period from date of first lenalidomide dose (baseline) until the date of death or last follow-up available at the time of the retrospective data collection (whichever occurs first) including for patients lost to follow-up or who discontinue the drug for any reason. Data collected at baseline will include those data that could have been generated earlier but are relevant at the baseline date (for example, information related to diagnosis).

Time to progression to AML or time to any other kind of event will be counted from the date of first lenalidomide dose (baseline).

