Lenalidomide and Risk of AML Progression in Patients with Transfusion-dependent IPSS Low- or Int-1–Risk MDS Del(5q)

A retrospective analysis was published (Kuendgen, 2012a) comparing the risk of progression to AML and OS in patients treated with lenalidomide (from Studies MDS-003 and MDS-004 combined (Fenaux, 2011; List, 2006) with that of similar patients from the Düsseldorf MDS Registry (previously described) who never received lenalidomide (Germing, 2012). The comparative study included only patients with transfusion-dependent anemia without concomitant thrombocytopenia (< $50,000/\mu$ L) or neutropenia (< $500/\mu$ L) to have comparable populations. Overall, the 2 cohorts included 295 lenalidomide-treated and 125 untreated patients.

To account for differences in person-time at risk in these 2 cohorts due to different starting points for follow-up (from diagnosis in the untreated cohort versus inclusion in the study for the treated cohort), *left truncation* was considered appropriate and adopted for all analyses in this study. The 2 cohorts were well balanced, except for a higher transfusion need for treated versus untreated patients (median of 6 versus 2 units of RBC/8 weeks); higher transfusion dependence is a well-known risk factor for progression to AML and reduced survival (Malcovati, 2006).

Based upon the competing-risk estimator with left truncation, the 2-year cumulative incidence of progression to AML was 6.9% and 12.1% for the cohort of treated versus untreated patients, respectively; the respective 5-year cumulative incidence was 22.8% and 19.9% (Kuendgen, 2012a). Two-year survival was 89.9% versus 74.4% in treated versus untreated patients. After adjustment for covariates, the risk of progression to AML was similar in the 2 cohorts (hazard ratio [HR] = 0.969), while the risk of death was significantly reduced in the lenalidomide-treated cohort (HR = 0.597, p = 0.012). The authors concluded that the treatment of patients with low- or int-1–risk MDS and del(5q) with lenalidomide did not increase the risk of progression to AML, but it possibly conferred a survival benefit in RBC transfusion-dependent patients with del(5q) low- or int-1–risk MDS.

A similar study previously compared the time to AML progression and survival in 95 low- or int-1–risk MDS del(5q) patients treated within the French ATU (Authorisation Temporaire d'Utilisation) cohort to 99 similar patients of the GFM (French MDS Group) who never received

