7.1.2 Selection Criteria

7.1.2.1 Inclusion Criteria

- Patients with MDS commencing their treatment with lenalidomide after the granting of Regulatory approval for use in the treatment of MDS in the EU (EC Decision, 13-Jun-2013) and a subsequent positive reimbursement decision in the countries concerned, irrespective if the initial MDS diagnosis occurred before (prevalent patients) or after (incident patients) such date with the exception of eligible patients from the company-sponsored Connect[®] Myeloid Disease Registry (US Cohort Registry) who will be included regardless of start date of treatment
- Laboratory confirmation (morphological and cytogenetic) of MDS
- Patients with confirmed date of MDS diagnosis and lenalidomide treatment initiation
- Obtaining appropriate permission from the selected data sources to utilise the data

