7.2 Setting

7.2.1 Study Population and Cohorts

Overall population: Those MDS patients who have received at least one dose of lenalidomide and who started their treatment after lenalidomide has obtained EU Regulatory approval for the MDS indication and in countries that granted a subsequent positive reimbursement decision with the exception of eligible patients from the company-sponsored Connect® Myeloid Disease Registry (US Cohort Registry) who will be included regardless of start date of treatment.

This population will include both prevalent (patients whose initial MDS diagnosis is **prior** to the date of EU-approval for the MDS indication, but whose initiation of lenalidomide treatment occurs on or after the date of EU-approval for the MDS indication) and incident patients (patients whose initial MDS diagnosis and initiation of treatment with lenalidomide is **after** the date of EU-approval for the MDS indication).

MDS licensed indication cohort (ie, on-label cohort): All patients with transfusion-dependent IPSS low- or int-1-risk MDS with isolated del(5q) in the EU who started their treatment after lenalidomide has obtained EU Regulatory approval for the MDS indication and in countries that gave a subsequent positive reimbursement decision.

Other MDS indication cohort (ie, off-label cohort): All patients with any type of MDS other than transfusion-dependent IPSS low- or int-1-risk MDS with isolated del(5q) in the EU who

started their treatment after lenalidomide has obtained EU Regulatory approval for the MDS indication and in countries that gave a subsequent positive reimbursement decision with the exception of eligible patients from the company-sponsored Connect[®] Myeloid Disease Registry (US Cohort Registry) who will be included regardless of start date of treatment.

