7.3 Variables

Variables to be considered in this analysis as baseline, exposure, treatment, and outcome variables are described in Table 3 (demographic and clinical variables), Table 4 (lenalidomide therapy and other treatment variables), and Table 5 (outcome variables for safety).

The following data variables will be collected from the registries according to local medical practice and availability of data.

Table 3:Demographics and Clinical Variables for Both On- and Off-label
Cohorts

Variables ^a	
Demographics	
Age	Age
Sex	Male/female
Country	Country
Clinical Variables (Baseline Ch	aracteristics)
Date of MDS Diagnosis	Date of initial MDS diagnosis
Date of First Dose of Lenalidomide	Date of first record of lenalidomide treatment initiation
Cytogenetic Abnormalities ^b	Karyotype information, method of diagnosis
Prior invasive malignancy	Yes/No and date/type of previous malignancy, previous therapy (yes/no/unknown for surgery, radiation, chemotherapy)
Bone Marrow and Peripheral Blood Morphology	Bone marrow blast count (%) – at baseline and until disease progression; other bone marrow findings according to the WHO classification: dysplasia by lineage, ringed sideroblasts/erythroid precursors, and Auer rods at baseline
Transfusion Burden	Transfusion burden (units/8 weeks); before lenalidomide treatment initiation and until PD or last follow-up date
Hemoglobin Level	Hemoglobin level; at baseline and every 6 months until PD or last follow-up date
Ferritin level	Ferritin level; at baseline
Platelet Count	Platelet count; at baseline and every 6 months until PD or last follow-up date
Neutrophil Count	Neutrophil count; at baseline and every 6 months until PD or last follow-up date
Endogenous EPO Level	EPO level; at baseline
Risk Classification	Classification as per IPSS

Variables ^a		
Relevant Medical History	Prior history of cardiovascular events (eg, angina/coronary artery disease, MI, CHF, arrhythmia, hypertension, peripheral arterial disease, cerebrovascular event); thromboembolic events (VTEs); pulmonary, hepatic, pancreatic or renal disease; diabetes; prior invasive malignancy, prior NMSC; past life-threatening illness in other organ system.	
Comorbidities	Current cardiovascular or cerebrovascular disease, chronic VTE, current pulmonary, hepatic, pancreatic or renal disease, diabetes, current life-threatening illness in other organ system	

Table 3: Demographics and Clinical Variables for Both On- and Off-label Cohorts

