7.4 Data Sources

Celgene assessed the feasibility of this protocol using various potential data sources across the EU for the identification of off-label prescriptions and existence of longitudinal data to measure long-term outcomes of patients with MDS, including progression to AML. The sources of data for the primary drug-utilisation objective and the secondary safety objectives in this study will include, but will not be limited to:

- the existing academic EUMDS Registry
- the Spanish Registry of MDS or RE SMD (registro español de síndromes mielodisplásicos), coordinated by the Spanish Group of MDS [GESMD] who aims to promote and develop primary research on MDS, bringing together all those involved in research, diagnosis and management of patients with MDS.
- the Düsseldorf MDS Registry, who aims, as best possible, to biologically characterize MDS, anticipate the course of the disease, and find the most suitable therapies as a benefit for all MDS patients
- the online French Registry of MDS, coordinated by the French MDS group [GFM]), a non-profit organization that includes most French haematology centres, several of them registered as centres of excellence of the International MDS Foundation
- the Danish National Acute Leukemia Registry.

Additionally, the company-sponsored Connect[®] Myeloid Disease Registry (US Cohort Registry) will be used to address the secondary safety objectives (but not the primary drug-utilisation objective due to a different MDS indication approved in the US, which is for the treatment of patients with *transfusion-dependent anemia due to low- or intermediate-1-risk myelodysplastic syndromes [MDS] associated with a deletion 5q abnormality with or without additional*

cytogenetic abnormalities). The company-sponsored Connect[®] Myeloid Disease Registry is a non-interventional, prospective, longitudinal, observational, multicenter, US cohort registry study of patients with confirmed cases of newly diagnosed MDS, idiopathic cytopenia of undetermined significance, and AML.

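### Event time runs from first lenalidomide dose, but registry entry by that dose is not required and no entry date is listed, so late entry can be neither detected nor corrected

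*Protocol*

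**What the plan says.** Protocol section 7.1.1 sets one time origin for everyone: "Time to progression to AML or time to any other kind of event will be counted from the date of first lenalidomide dose (baseline". Data are collected "to cover the period from date of first lenalidomide dose (baseline) until the date of death or last follow-up available" at the time of extraction, so the observation window opens on the same day. The Abstract repeats both rules.

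Among the inclusion criteria in section 7.1.2.1, the one on dates asks for "Patients with confirmed date of MDS diagnosis and lenalidomide treatment initiation". Neither this list nor the exclusion list in 7.1.2.2 relates registry enrolment to first dose.

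Table 3 (section 7.3) records the date of initial MDS diagnosis and, for treatment, "Date of first record of lenalidomide treatment initiation". Table 5 adds dates for AML, death, adverse events and second primary malignancies. None of Tables 3 to 5 lists the date on which the patient entered the registry.

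Sections 7.6 and 7.7.3 have each registry run the AML Kaplan-Meier and Cox analyses on its own data under common sponsor instructions. Section 7.9 says raw data cannot be pooled. The limitations there cover missing data, loss to follow-up, visit intervals and cytogenetic misclassification, but not entry after treatment start.

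**The concern.** A patient enrolled some months after first dose is in the data only because he or she reached enrolment. If enrolment required being alive and free of AML, no AML event or death could have been observed between dose and enrolment. Counting that interval as time at risk adds person-time without possible events. AML incidence and mortality then come out too low, and survival too high.

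The Abstract names incidence of and time to AML in off-label patients as the main secondary objective, and on- versus off-label hazard ratios are planned. In a post-authorisation safety study, an understated AML rate errs in the reassuring direction. If late entry were more common in one label cohort than in the other, the hazard ratio within a registry would be distorted too.

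The background in section 5.2 shows that the tool is familiar. One cited comparison adopted left truncation "To account for differences in person-time at risk in these 2 cohorts due to different starting points for follow-up", and a second did likewise.

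**Working it through.** **The plan's own figures.** The protocol gives no figure for late entry. The figure that sets the scale is the AML interval in section 7.5: 17% of 230 off-label patients, 95% CI 12.3% to 22.4%. Since 0.17 × 230 = 39.1, take 39 events. The exact binomial (Clopper-Pearson) interval for 39/230 is 12.34% to 22.44%, which reproduces it.

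**Check 1: AML rate, fixed delay.**

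Inputs:
- 2-year AML risk of 16.8% in the combined lenalidomide arms of the phase 3 study (section 5.2), taken as a constant hazard: λ = −ln(1 − 0.168)/2 = 0.0920 per year.
- Assumed: every patient is followed to 3 years after first dose; deaths are ignored.
- Assumed: a share q of included patients entered d years after first dose and were free of AML at entry.

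Expected person-time at risk over T years is P(T) = (1 − e^(−λT))/λ:
- P(3) = 2.622
- P(2.5) = 2.233
- P(2) = 1.827

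True time at risk per patient is A = (1 − q)·P(3) + q·P(3 − d). Counting from first dose adds q·d with no possible event. The events are the same either way, so naive rate / true rate = A/(A + q·d).

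| q | d (years) | A | A + q·d | Ratio | AML rate too low by |
|---|---|---|---|---|---|
| 20% | 0.5 | 2.544 | 2.644 | 0.962 | 4% |
| 20% | 1.0 | 2.463 | 2.663 | 0.925 | 8% |
| 40% | 0.5 | 2.466 | 2.666 | 0.925 | 8% |
| 40% | 1.0 | 2.304 | 2.704 | 0.852 | 15% |

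With q = 0 the ratio is 1.

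**Check 2: simulation with deaths and spread-out delays.** The AML hazard again gives 16.8% at 24 months. Death is exponential with a median of 42 months (section 5.2 reports arm medians of 35.5 to 44.4), so true 24-month survival is 2^(−24/42) = 67.3%. Each scenario has 600,000 patients. A share q has an entry delay uniform over the range shown and is included only if alive and AML-free at entry. Naive estimates count risk from first dose.

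| q | Delay (months) | Naive 24-month AML | Naive 24-month survival |
|---|---|---|---|
| 10% | 0–6 | 16.6% | 67.5% |
| 10% | 0–12 | 16.4% | 67.8% |
| 25% | 0–12 | 15.9% | 68.9% |
| 50% | 0–12 | 15.0% | 70.5% |
| 50% | 0–24 | 13.4% | 73.3% |

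With the time origin kept at first dose but risk starting at registry entry, the late-entry scenarios return 24-month AML of 16.7% to 16.9% and survival of 67.1% to 67.4%, the true values to within simulation error.

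**The case against.** **Late entry is not documented.** This stands. Nothing in the protocol says that any patient enrolled after first dose, and both the shares and the delays above are assumptions. A reader might take two features as evidence of late entry, but neither supports it:
- Prevalent patients are prevalent by diagnosis, "but whose initiation of lenalidomide treatment occurs on or after the date of EU-approval for the MDS indication". An earlier diagnosis does not imply enrolment after the dose.
- US patients "who will be included regardless of start date of treatment" are exempted from the rule tied to EU approval, which says nothing about dose relative to enrolment. Section 7.4 describes that source as a prospective "US cohort registry study of patients with confirmed cases of newly diagnosed MDS, idiopathic cytopenia of undetermined significance, and AML", which if anything makes entry after first dose less likely.

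**First dose is a proper origin for treated patients.** This also stands. The rule in 7.1.1 is not the error in itself; what is missing is an entry rule for the risk period. Nor does the protocol contradict its background. In the first cited comparison the two cohorts had different starting points (diagnosis versus study inclusion), and the second gives a similar reason. Here both cohorts share one origin.

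**The direction is not assured for AML.** Being alive at enrolment does not exclude an earlier AML, which could be recorded retrospectively. The sources include an acute leukaemia registry and a US registry that also enrols AML. If AML prompts capture, the bias could run upward. The downward figures hold only if entry requires being AML-free.

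**The size is modest.** With 25% entering over 0 to 12 months, 24-month AML moves from 16.8% to 15.9%. That is small beside an interval of 12.3% to 22.4%. It is a systematic shift, however, and more patients would not remove it.

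**Delayed entry may be in the SAP.** The SAP is not shown, and the registries could use enrolment dates they hold without transferring them. This weakens the point. But the time origin, the eligibility criteria and the common variable list are all set in this protocol, and because raw data cannot be pooled, the sponsor could not easily repair the omission afterwards.

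**Conclusion.** The point holds as a gap in what the protocol fixes, not as a demonstrated bias. Event time and follow-up start at first dose, registry entry by that dose is not required, and no entry date is listed. Late entry is therefore permitted and, from the listed variables, cannot be detected or corrected.

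The size is conditional. If 20% to 40% of patients entered 6 to 12 months late and had to be alive and AML-free to enter, the AML rate would be about 4% to 15% too low. Across the simulated late-entry scenarios, naive 24-month AML lies between 16.6% and 13.4% against a true 16.8%. The bias is nil without late entry and could reverse where AML triggers capture.

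A reader might infer that survival estimates would also be too low. The opposite holds: mortality is understated, and 24-month survival rises from 67.3% to as much as 73.3%. Survival is not a stated objective, and the planned Kaplan-Meier and Cox analyses concern AML, so the consequence lies mainly there. The change is worth making because it is cheap, not because the protocol shows that harm has occurred.

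**What to change.** - Keep first dose as time zero.
- Add the registry-entry date to the common variable set (Table 3).
- Ask each registry to report how many patients entered after first dose, by on- and off-label cohort.
- In the AML Kaplan-Meier, cumulative-incidence and Cox analyses, start each patient's risk period at the later of first dose and registry entry, and put this in the common instructions to the registries.

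The cost is one date field and an entry-time option in standard survival software. Nothing changes for patients enrolled by first dose. The downside is slightly less early person-time and the loss from these analyses of AML events recorded before entry. Listing those events separately would show whether any source captures patients because of AML.
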